Gastrointestinal problems, such as gastroesophageal reflux disease (GERD) are common in T2D.¹⁴ A recent meta-analysis involving 9,067 cases and 81,968 controls showed a significant association between diabetes and the risk of GERD.¹⁵ The prevalence of GERD symptoms in patients with T2D could be as high as 40%.¹⁴ Therefore, millions of individuals are managing blood glucose and GERD concomitantly.¹⁶ Proton pump inhibitors (PPIs) are the medications of choice for GERD, and are primarily metabolised by CYP2C19.¹⁷ The potential for drug-drug interactions is highest for omeprazole and its stereo-isomer esomeprazole, which are metabolised almost entirely by CYP2C19.^{17,18} Furthermore, it has been shown that impact of PPIs on the PK, PD, and therapeutic response to drugs metabolised by CYP2C19 could depend on *CYP2C19* genotype, with highest effect seen in CYP2C19 normal metabolisers (extensive metabolisers, EM)^{19,20} and ultrarapid metabolisers (UM).²¹

Project aims

Considering the high prevalence of use of PPIs,²² the greater incidence of GERD in T2D and likely high concomitant use of PPIs with gliclazide, and the possibility of their interaction via CYP2C19, the primary aim of this pilot clinical study is to explore potential drug-drug interaction between gliclazide and omeprazole in CYP2C19 EM/UM metabolisers. The specific aims are:

1. To explore whether gliclazide PK is altered upon co-administration with omeprazole in healthy volunteers, CYP2C19 EM/UM metabolisers
2. To explore whether gliclazide PD is altered upon co-administration with omeprazole in healthy volunteers, CYP2C19 EM/UM metabolisers

Preliminary data

To our knowledge, there have been no studies exploring potential interaction between any PPI and gliclazide, in animals or humans. To explore this possible drug-drug interaction, we performed preliminary observational analyses in the large population-based GoDARTS study (UK). Briefly, our preliminary data suggest that co-treatment with PPIs, especially omeprazole, increases the risk of hypoglycaemia in patients with CYP2C19 EM/UM phenotype treated with gliclazide. This has been confirmed by better glycaemic response (lower HbA1c) associated with PPI use in EM/UM patients treated with gliclazide. These results support a biologically plausible hypothesis of possible interaction between PPIs and gliclazide, in relation to CYP2C19 genotype.

Study population

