Exclusion criteria for drug interaction study

- abnormalities in physical examination, ECG and routine clinical laboratory tests (including fasting blood glucose concentration)
- medication use during the 14 days prior and during the study periods
- grapefruit, grapefruit juice, alcohol, beverages or food containing methylxanthines use during 72 h prior and during the study periods

Participants will be randomised to specific treatment sequences using SAS Proc Plan procedure.

Drug interaction study design

A randomised, placebo controlled, two-sequence, two-period crossover study, with at least a 7-day washout period between the study periods will be conducted to compare the effects of gliclazide (40 mg, half of an 80 mg tablet of Diprian[®], Hemofarm d.o.o. Banja Luka, B&H, orally) and placebo with those of gliclazide combined with omeprazole (20 mg, Ulcosan[®], Bosnalijek d.d. Sarajevo, B&H, orally). Prior to administration of gliclazide, omeprazole or placebo will be administered once daily at 8 AM for 4 days (on day 1 until day 4) to assure PD steady-state. At 8 AM of the day 5, after an overnight fast (last meal at 9 pm of the previous day), the participants will be given a single dose of 40 mg gliclazide with 240 mL of water together with omeprazole or with placebo according to their treatment assignment.

The volunteers will be given both drugs (gliclazide + omeprazole or gliclazide + placebo) in a sitting position and they will not be permitted to lie down or sleep for the next 4 h after taking gliclazide. They will be under direct medical supervision throughout the 24 h following drug administration.

In order to counteract the blood glucose-lowering action of gliclazide, subjects will receive standardized meals: a breakfast at 30 min after gliclazide intake, snacks after 2 and 3 h, a lunch (warm meal) after 4 h, a snack after 6 h, a dinner after 8 h, and additional snacks at 10 h and 12 h after drug administration. The larger meals should be eaten within 10 minutes, and snacks within 5 minutes. No other food and drink (with the exception of water) or strenuous activities will be allowed.

[figure not shown]
Schematic design of the drug interaction study

- Period 1
 - Eight (8) subjects will receive treatment A on days D 1–5
 - Eight (8) subjects will receive treatment B on days D 1–5
- Wash-out period D6–14
- Period 2
 - Eight (8) subjects will receive treatment B on days D 15–19
 - Eight (8) subjects will receive treatment A on days D 15–19

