PK parameters will be calculated by a noncompartmental analysis using PKSolver a program for PK and PD data analysis in Microsoft Excel. Gliclazide maximum concentration (C_{max}) and time to reach C_{max} (t_{max}) will be determined by the inspection of the concentration–time data. The area under the plasma gliclazide concentration–time curve (AUC) up to the last concentration measured (AUC_{0-t}) will be determined using the linear trapezoidal rule. The AUC will be extrapolated to infinity ($\text{AUC}_{t-\infty}$) using C_t/k_{el} , where C_t is the last measured gliclazide concentration and k_{el} is the elimination rate constant that will be estimated from the slope of the best-fit line determined by linear regression analysis of the log-transformed concentration-time curve. The elimination half-life ($t_{1/2}$) will be calculated using the following equation: $t_{1/2}=\ln(2)/k_{\text{el}}$. The apparent oral clearance (CL/F) will be calculated as $\text{dose}/\text{AUC}_{0-\infty}$. The apparent volume of distribution ($V_{\text{d}/\text{F}}$) will be calculated as $\text{dose}/\text{AUC} \times k_{\text{el}}$.

Pharmacodynamic parameters

- C_{\min} : Glucose minimum concentration
- $C_{\text{avg } 0-4}$: Average glucose concentration in the period 0–4 h
- $C_{\text{avg } 0-12}$: Average glucose concentration in the period 0–12 h
- AUC_{0-4} : Area under the glucose concentration–time curve from 0 to 4 h
- AUC_{0-12} : Area under the glucose concentration–time curve from 0 to 12 h

- C_{\min} : Insulin minimum concentration
- $C_{\text{avg } 0-4}$: Average insulin concentration in the period 0–4 h
- $C_{\text{avg } 0-12}$: Average insulin concentration in the period 0–12 h
- AUC_{0-4} : Area under the insulin concentration–time curve from 0 to 4 h
- AUC_{0-12} : Area under the insulin concentration–time curve from 0 to 12 h

To compare the PD effects of gliclazide, the areas under the glucose and insulin concentration–time curve from 0 to 4, and 0 to 12 h after the administration of gliclazide will be calculated using the linear trapezoidal rule. The minimum glucose and insulin concentration will be determined by observation of the concentration–time data, and mean concentrations from 0 to 4 h and from 0 to 12 h will be calculated by dividing the area under the glucose/insulin concentration–time curve by the corresponding time interval.

Safety assessment and precaution measures

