The volunteers will undergo a detailed physical, ECG, and laboratory examination upon inclusion in the drug interaction study. The subjects will be contacted within 14 days of study completion in order to confirm the adequate post-study status.

If any clinical reasons arise that could endanger health status of the subjects by taking blood samples, the blood samples will not be drawn. Considering that bruising, bleeding, infection or pain may occur at the site of venepuncture and cannulation, these procedures will be performed by experienced medical staff to minimise the risk of excessive bleeding or bruising, and a topical anaesthetic may be used, if required, to reduce the pain.

Since this combination of drugs can potentially induce risk of hypoglycaemia, administration of the two drugs will be carried out in the hospital where the subjects will be hospitalised for 24 h and will be continuously under direct medical supervision. In order to avoid the risk of hypoglycaemia, subjects will receive 8 meals (breakfast, lunch, dinner and 5 snacks). In case of any symptom suggestive of hypoglycaemia (nervousness, sweating, intense hunger, trembling, weakness, palpitations), the blood glucose level will be measured using a glucometer and one of the standard measures of raising blood sugar will be applied, such as administration of 20% oral glucose solution, glucose solution for intravenous use, or glucagon for intramuscular use.

In addition, systolic and diastolic blood pressure and heart rate will be measured in the supine position after a 5-minute rest, before drug intake and during the PK profiles at 2, 4, 12 and 24 hours after gliclazide administration.

Power analysis

For identification of clinically relevant drug-drug interaction, we will use the bioequivalence approach. The main outcome to be evaluated is the exposure to gliclazide, expressed as AUC_{0-t} . Sample size calculation was performed using SAS Proc Power procedure for equivalence test in 2x2 crossover design.²⁵ For an equivalence range of 80–125%, the within-subject coefficient of variation for the AUC values for gliclazide of 7.8% based on previous PK studies,^{26,27} and expected test/reference geometric

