mean ratios between 87–115%, 14 volunteers (7 individuals per sequence) are required to show the lack of interaction with 85% power. To account for potential drop-outs due to non-compliance or loss of follow up (assuming a drop-rate of 10%), a total of 16 subjects, CYP2C19 EM/UM metabolisers, will be randomised. To achieve this number, minimally 40 volunteers will be initially recruited.

Statistical analysis

The geometric mean will be calculated for each PK and PD parameter. Logarithmic transformation will be used for PK variables, except t_{max} , before the analysis. The ratios of the geometric means with 90% confidence intervals (CI) will be assessed by linear mixed models between the two treatment assignments: gliclazide and omeprazole coadministration to that of gliclazide and placebo. The statistical analyses will be performed using the SAS 9.3 software (SAS Institute Inc., Cary, NC).

Original scientific contribution and clinical significance of the research

This research will establish whether omeprazole can alter PK/PD of gliclazide, and thus increase the risk of serious hypoglycaemia with this recommended SU drug.

This study can unravel new, previously unrecognized drug-drug and drug-drug-gene interactions. If clinically relevant alterations in gliclazide PK/PD parameters are established, our findings can lead to changes in clinical practice with the aim of preventing serious, potentially life-threatening hypoglycaemia induced by gliclazide treatment.

Confidentiality and data protection

All clinical, laboratory and genetic data will be processed in a manner designed to protect the identity of the participants, in accordance with the rules of personal data protection and the guidelines of the Good Clinical Practice. Participants' privacy will be respected in all published and other public written data that will result from this study.

Withdrawal from the study

Participants are free to withdraw from the study at any time, without obligation to explain their decision.

Insurance

In accordance with the guidelines of Good Clinical Practice, the subjects will be insured under the terms of insurance for Clinical Trials.

Compensation of costs

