The costs of participants arising from their participation in the screening visit will be reimbursed in the amount of 50.00 BAM upon completion, and the costs of participants arising from their participation in the drug interaction study will be reimbursed in the amount of 400.00 BAM upon completion of the study. The funds will be paid to the participants' bank account.

Adverse events

Definitions

An *adverse event* (AE) is any untoward medical event affecting a clinical trial participant. Each initial AE will be considered for severity, causality or expectedness and may be reclassified as a serious event or reaction based on prevailing circumstances.

An *adverse reaction* (AR) is where it is suspected that an AE has been caused by a reaction to a trial drug.

A serious adverse event (SAE), serious adverse reaction (SAR) or suspected unexpected serious adverse reaction (SUSAR) is any AE, AR or UAR that at any dose:

- results in death or is life threatening
- requires hospitalisation or prolongation of existing hospitalisation
- results in persistent or significant disability or incapacity
- is a congenital anomaly or birth defect.

Recording and reporting adverse events and serious adverse events

The principal investigator should report any SAE that is both related to the research procedures and is unexpected, to the Ethics Committees which approved the study, and to the Faculty of Pharmacy University of Sarajevo, within 24 hours of the becoming aware of the event.

An adverse event log will be maintained in the CRF. The principal investigator on this study is medically qualified and will assess all adverse events for expectedness, seriousness and causality and will follow up to resolution or to within 30 days of the end of the study. The seriousness of the adverse event will be graded according to the *Common Terminology Criteria for Adverse Events (CTCAE) v5.0 Publish Date: November 27, 2017* (https://ctep.cancer.gov/protocoldevelopment/electronic_applications/docs/CTCAE_v5_Quick_Reference_5x7.pdf).

References

1. Feng, Y., *et al.* Ser1369Ala variant in sulfonylurea receptor gene ABCC8 is associated with antidiabetic efficacy of gliclazide in Chinese type 2 diabetic patients. *Diabetes Care* **31**, 1939-1944 (2008).
2. Standards of Medical Care in Diabetes-2017: Summary of Revisions. *Diabetes Care* **40**, S4-S5 (2017).

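### Do the glucose and insulin results need a separate rule for samples taken after rescue for hypoglycaemia?

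*Combined protocol and SAP*

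**What the plan says.** Under Safety assessment and precaution measures, symptoms suggestive of hypoglycaemia lead to rescue: "the blood glucose level will be measured using a glucometer and one of the standard measures of raising blood sugar will be applied". The measures named are oral glucose, intravenous glucose and intramuscular glucagon.

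Under Pharmacodynamic parameters, the glucose and insulin areas from 0 to 4 h and from 0 to 12 h "after the administration of gliclazide will be calculated using the linear trapezoidal rule". Average concentrations are those areas divided by the length of the interval, and minima are read from the data. Statistical analysis adds: "The geometric mean will be calculated for each PK and PD parameter". It then gives ratios of geometric means with 90% confidence intervals from linear mixed models.

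Drug interaction study design fixes the meals and adds: "No other food and drink (with the exception of water) or strenuous activities will be allowed". On safety recording, the protocol says: "An adverse event log will be maintained in the CRF".

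Power analysis names the outcome on which the study is sized: "The main outcome to be evaluated is the exposure to gliclazide, expressed as" AUC0–t. The pharmacodynamic question is the second specific aim: "To explore whether gliclazide PD is altered upon co-administration with omeprazole in healthy volunteers, CYP2C19 EM/UM metabolisers".

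**The concern.** Rescue is the one unscheduled glucose input that the protocol allows on the dosing day, and it may not be balanced between treatments. Preliminary data reports that "co-treatment with PPIs, especially omeprazole, increases the risk of hypoglycaemia in patients with CYP2C19 EM/UM phenotype treated with gliclazide". If the same held in these volunteers, rescue could be more frequent in the omeprazole period. The added glucose would then lift AUC and average concentration in the very period where a fall is expected, moving a ratio below 1 back towards 1. Rescue glucose would also tend to raise insulin, which could exaggerate an insulin effect.

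The plan does not say whether post-rescue samples are kept, set aside or examined separately, and it does not plan a count of rescues by treatment. At stake is the reading of a null glucose result under aim 2: it might reflect no interaction, or a real fall partly offset by rescue.

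**Working it through.** **The plan's own figure.** The sample size rests on gliclazide AUC0–t: limits 80–125%, within-subject CV 7.8%, ratio 87–115%, 14 evaluable subjects, 85% power. On the log scale σ = √ln(1 + 0.078²) = 0.0779, SE = 0.0779 × √(2/14) = 0.0294, with 12 degrees of freedom. Two one-sided 5% tests (the 90% interval read that way) give exact power of 85.05% at 0.87 and 84.7% at 1.15. Then 14/0.90 = 15.6, rounded up to 16. The figure reproduces, and no glucose or insulin value enters it.

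**Size of the glucose shift.** The documents supply 16 subjects, the two windows and the sampling times. The rest is assumed: mean glucose m of 5–6 mmol/L, and a = 1.5–3.5 mmol·h/L added per rescue, all inside the window. Let k be the number rescued on omeprazole minus the number rescued on placebo, and T the window in hours. Then

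shift = exp[(k/16) × ln(1 + a/(m×T))] − 1.

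Example: m = 5, T = 4, a = 3.5, k = 4 gives exp[0.25 × ln(1.175)] − 1 = 4.11%.

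| Mean glucose, window | k = 1 | k = 2 | k = 4 |
|---|---|---|---|
| 5 mmol/L, 0–4 h | 0.45–1.01% | 0.91–2.04% | 1.82–4.11% |
| 6 mmol/L, 0–4 h | 0.38–0.85% | 0.76–1.72% | 1.53–3.46% |
| 5 mmol/L, 0–12 h | 0.15–0.35% | 0.31–0.71% | 0.62–1.43% |
| 6 mmol/L, 0–12 h | 0.13–0.30% | 0.26–0.60% | 0.52–1.19% |

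Average concentration is AUC divided by a constant, so it shifts by the same percentages. A rescue after 4 h leaves the 0–4 h measures unchanged.

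**Net rescues needed to hide a 5% fall** (m = 5): k = 16 × ln(1/0.95) / ln(1 + a/(5T)). For 0–4 h this is 5.1 (a = 3.5) to 11.3 (a = 1.5), so 6 to 12 of the 16 subjects. For 0–12 h it is 14.5 to 33, so at least 15 of 16 or out of reach.

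**Sensitivity to the assumptions.** Take instead a flat 5 mmol/L reference, a true ratio of 0.90, and rescue at 2 h with a triangular excursion peaking at 2–6 mmol/L over 1.5–2 h, sampled at the protocol's times. For the largest excursion (area 6 mmol·h/L) a rescued subject's 0–4 h ratio is (0.90 × 20 + 6)/20 = 1.20. Four such subjects of 16 give exp[(4 ln 1.20 + 12 ln 0.90)/16] = 0.967. Across these excursions:

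- 1–2 excess rescues: 0.904–0.933 (0–4 h) and 0.901–0.912 (0–12 h).
- 4 excess rescues: 0.916–0.967 and 0.906–0.924.
- 8 excess rescues: 0.933–1.039 and 0.911–0.949.

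Sampling is every 2 h from 8 h, so a late rescue is caught unevenly. A 1.5 h triangle of height h has area 0.75h. The trapezoid credits it with 2h if its peak falls on the 10 h sample (2/0.75 = 2.7 times too much), and with 0 if it falls between samples. At m = 5, a = 3.5 and k = 4, all peaking at 10 h, the 0–12 h shift would be exp[0.25 × ln(1 + 3.5 × 2.667/60)] − 1 = 3.7%. The 0–12 h range in the table is therefore not a hard bound.

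**Glucose minimum.** Keeping later samples cannot raise a minimum. Rescue may stop a further fall, but no rule for handling samples recovers the value that would have been reached.

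**The case for a change.** The best argument for a change is timing. A choice about which samples count is neutral only if made before the data are seen, and in 16 subjects a few rescues could tempt someone to choose afterwards. The protocol itself foresees hypoglycaemia with this combination and says that its findings may lead to changes in practice. A sentence, a table and one sensitivity analysis on the pre-rescue window would cost little.

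Part of this stands. The text does not say in terms that post-rescue samples are kept, and the direction of the glucose shift is right if omeprazole lowers glucose. The rest is weaker.

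- **A default already exists.** Full fixed windows with no exclusion mean that all scheduled samples count. Dropping some would be the departure that needs justifying.
- **The alternative is not clearly better.** Cutting each rescued subject's window at rescue makes its length depend on the outcome, stops follow-up where glucose is falling, and mixes short with full windows. It does not isolate the drug effect and may still understate it.
- **A null result would not stand alone.** Symptomatic hypoglycaemia under supervision would ordinarily count as an adverse event, and a dated log entry identifies the treatment period. Gliclazide exposure, the main outcome, is read beside it. The case report form is not in the documents, so rescue fields cannot be said to be missing.
- **A rescue table would describe, not test.** Four subjects rescued only on omeprazole against none only on placebo gives an exact two-sided paired P of 2 × 0.5⁴ = 0.125.

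**Conclusion.** No change is needed. This is unstated detail that the ordinary reading of the plan settles: as-observed glucose and insulin over the stated windows, which is a legitimate quantity under study conditions, rescue included.

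The bias needs four things together: rescue occurs, it is more frequent on omeprazole, it falls inside the window, and the true glucose ratio is below 1. The subjects are healthy men aged 18–30 given a single 40 mg dose with eight scheduled meals and snacks, and the symptoms that trigger rescue are non-specific enough to arise on placebo too. The support for unequal risk is observational and comes from treated patients.

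Under the first set of assumptions, 1 to 4 net rescues shift the ratio by at most 4.1% over 0–4 h and 1.4% over 0–12 h. Larger or badly timed excursions give more, so calling the shift small is a judgement about how rare rescue will be. It cannot be derived from the documents. The insulin shift would tend upward and is not quantified. Aim 2 is exploratory, with no power calculation or separate decision rule of its own. Gliclazide AUC0–t, the 14 evaluable and 16 randomised subjects, and rescue care are unaffected.

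### Does using a bioequivalence test to identify an interaction leave a failed test open to being read as an interaction?

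*Combined protocol and SAP*

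**What the plan says.** The Power analysis section introduces the method with "For identification of clinically relevant drug-drug interaction, we will use the bioequivalence approach". It names AUC0-t as the outcome ("The main outcome to be evaluated is the exposure to gliclazide") and states "Sample size calculation was performed using SAS Proc Power procedure for equivalence test in 2x2 crossover design". The inputs are limits of 80–125% and "the within-subject coefficient of variation for the AUC values for gliclazide of 7.8% based on previous PK studies". The section concludes, for expected geometric "mean ratios between 87–115%, 14 volunteers (7 individuals per sequence) are required to show the lack of interaction with 85% power". Sixteen are randomised to allow for 10% drop-out.

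The Statistical analysis section plans ratios of geometric means, gliclazide with omeprazole against gliclazide with placebo, with 90% CIs from linear mixed models. It attaches no pass/fail rule to the interval.

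The Project aims section calls the study a pilot meant to explore a potential interaction. The section on scientific contribution and clinical significance says: "If clinically relevant alterations in gliclazide PK/PD parameters are established, our findings can lead to changes in clinical practice".

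**The concern.** One sentence assigns the equivalence test to finding an interaction, and the sample-size statement that follows powers it for the opposite conclusion. A 90% CI inside 80–125% supports the absence of a relevant interaction. A CI that is not inside the limits may mean that the true ratio lies beyond a limit. It may also mean that the ratio lies within the limits but close to one, or that variability was larger than planned. If all three were reported as an interaction, that positive claim would have no controlled error rate.

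This would matter because the team is looking for an interaction. The Preliminary data section describes more hypoglycaemia and lower HbA1c with PPI use in EM/UM patients on gliclazide, and the significance section mentions changes in practice. An unsupported positive claim could carry weight.

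**Working it through.** **Inputs.** From the Power analysis section: limits 0.80 and 1.25, within-subject CV 7.8%, N = 14 evaluable (16 randomised), expected ratio 0.87–1.15. The Statistical analysis section gives a 90% CI, which corresponds to two one-sided tests at 5% each.

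**Formulas** (2x2 crossover, log scale).

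- Within-subject SD = √ln(1 + 0.078²) = 0.0779.
- SE of the log ratio = 0.0779 × √(2/14) = 0.0294, with 14 − 2 = 12 degrees of freedom.
- t(0.95; 12) = 1.782.
- The 90% CI is the estimate divided and multiplied by exp(1.782 × 0.0294) = 1.054, at the planned SD.

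**The plan's own figure.** Exact power for two one-sided tests at N = 14 is 85.05% at a ratio of 0.87 and 84.7% at 1.15, which matches the stated 85%. N = 12 gives 79.1% and 78.7%. For drop-out, 14/0.90 = 15.6, rounded up to 16. The sample size reproduces.

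**What the planned interval can show.** With the multiplier of 1.054, an observed ratio between 1 and 1.25/1.054 = 1.19 puts the CI inside the limits. One above 1.25 × 1.054 = 1.32 puts it wholly above 125%. Values between 1.19 and 1.32 give an interval that straddles the limit. The table also allows for sampling error in the SD (N = 14, CV 7.8%).

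| True ratio | Equivalence not shown | CI wholly above 125% | CI straddles a limit |
|---|---|---|---|
| 1.00 | about 0% | about 0% | about 0% |
| 1.05 | about 0% | about 0% | about 0% |
| 1.10 | 0.7% | about 0% | 0.7% |
| 1.15 | 15.3% | about 0% | 15.3% |
| 1.20 | 63.2% | 0.2% | 63.0% |
| 1.24 | 91.7% | 2.9% | 88.9% |
| 1.25 | 95.0% | 5.0% | 90.0% |
| 1.30 | 99.8% | 34.9% | 64.9% |
| 1.35 | about 100% | 79.3% | 20.7% |
| 1.40 | about 100% | 97.6% | 2.4% |

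By symmetry on the log scale, the same holds for reciprocal ratios below 1. If all 16 are evaluable, equivalence is not shown in 10.9% at 1.15 and 59.3% at 1.20, and the CI lies wholly above 125% in 38.6% at 1.30 and 98.8% at 1.40.

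**If the CV is larger.** CVs of 15% and 20% are assumptions; the documents give only 7.8%. With N = 14, equivalence would not be shown in 3.8% at a ratio of 1.00 with CV 15%, 31% at 1.10 with CV 15%, and 25% at 1.00 with CV 20%. With N = 16 the last figure is 17%.

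**Reading the table.** The first numeric column is the concern: at 1.20 or 1.24, inside the limits, failure is common. The other two columns are the answer. Nearly all of those failures are straddling intervals, and they look different from an interval lying beyond the limit. Both are visible in the ratio and 90% CI that the plan already commits to reporting. A claim of interaction beyond the limit, made only when the whole CI lies above 125%, has a 5% error rate at a true ratio of 1.25.

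**The case for a change.** The strongest case for a change is that equivalence is the only framework named and that it is labelled as the tool for identification. A reader could infer that failing it identifies an interaction. No power is given for a positive finding. At a true ratio of 1.30 the interval straddles 125% in about 65% of trials, so a moderate interaction would fall where the plan is silent. A few sentences written before the data are seen would cost nothing.

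Part of this stands. The word chosen is loose, and no conclusion is written for an interval that is not wholly inside the limits.

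The rest does not stand. The documents contain no rule that equates failure with an interaction. The 80–125% range appears only among the sample-size inputs, and the power statement draws the right inference from an equivalence test. Nor do the documents predict a failed test. The preliminary data are observational associations with hypoglycaemia and HbA1c and give no exposure ratio. The only exposure ratio the plan expects is 87–115%, inside the limits, and the 15% failure at 1.15 is simply the complement of the planned 85% power. The sentence on clinical practice is conditional and is not part of the analysis plan. Finally, one tempting addition has its own cost: with no effect at all, a 90% CI excludes 100% in 10% of trials (5% on each side).

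**Conclusion.** The concern identifies missing detail, not an error. The plan uses one loose word and leaves unstated how to read a 90% CI that is not wholly within 80–125%. The practical ambiguity is confined to true ratios of about 1.15 to 1.30 and the mirror range below 1. It would widen only if the CV were well above 7.8%, which nothing in the documents suggests. At the planned CV, equivalence practically never fails when there is no effect.

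Followed as written, the analysis yields the geometric mean ratio and its 90% CI. An analyst can read the three outcomes directly from that interval: wholly inside, wholly outside, or straddling a limit and so inconclusive on clinical relevance. Writing the reading down would change no estimate, interval, sample size or stated figure. For a self-described pilot, this is a gap that competent analysts fill sensibly, and no change to the plan follows. This rests on the planned CV, on 14 to 16 evaluable volunteers, and on the ratio and interval being reported in full as the Statistical analysis section intends.
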